4.1.1 Testing strategy to account for multiplicity considerations

A hierarchy testing strategy will be applied to the following two-sided hypotheses testing for the primary (annual asthma exacerbation rate) and 2 key secondary endpoints (the change in pre-bronchodilator FEV₁ and total asthma symptom score from baseline to Week 48, respectively) for patients with baseline blood eosinophil counts $\geq 300/\mu\text{L}$.

Primary endpoint:

H01: annual asthma exacerbation rate ratio over 48 weeks (benralizumab/placebo) = 1

versus

H11: annual asthma exacerbation rate ratio over 48 weeks (benralizumab/placebo) $\neq 1$

The direction of superiority of benralizumab is indicated by a rate ratio less than 1.

Key secondary endpoints:

H02: Difference in mean change from baseline in pre-bronchodilator FEV₁ at Week 48 (benralizumab minus placebo) = 0

Versus

H12: Difference in mean change from baseline in pre-bronchodilator FEV₁ at Week 48 (benralizumab minus placebo) ≠ 0

The direction of superiority of benralizumab is indicated by a difference in means greater than 0.

H03: Difference in mean change from baseline in bi-weekly mean total asthma symptom score at Week 48 (benralizumab minus placebo) = 0

versus

H13: Difference in mean change from baseline in bi-weekly mean total asthma symptom score at Week 48 (benralizumab minus placebo) ≠ 0

The direction of superiority of benralizumab is indicated by a difference in means less than 0.

The overall type 1 error rate, will be strongly controlled at the 2-sided 5% significance level across the primary and key secondary endpoints. This testing strategy will be according to the following gatekeeping procedure:

Step 1: Perform the test of annual asthma exacerbation rate (H01 vs. H11) at the 2-sided 5% significance level. If the p-value is less than 0.05, then proceed to Step 2; otherwise, null hypothesis H01 is not rejected.

Step 2: Test the 2 key secondary endpoints simultaneously at the overall 2-sided 5% significance level using a Holm Procedure ([Holm 1979](#)). Let smaller p-value and larger p-value denote the ordered unadjusted p-values from these 2 endpoints.

Step 2a: If the smaller p-value is less than 0.025, then reject the corresponding null hypothesis and continue to *Step 2b*; otherwise stop and both null hypotheses of the 2 key secondary endpoints (H02 and H03) are not rejected.

Step 2b: If the larger p-value is less than 0.05, then reject the corresponding null hypothesis (i.e., both null hypotheses H02 and H03 are rejected); otherwise, the corresponding null hypothesis is not rejected (i.e., only the null hypothesis corresponding to the smaller p-value is rejected).

4.2 Analysis methods

4.2.1 Patient disposition

Patient disposition will be summarised using the all patients analysis set. The total number of patients will be summarised for the following categories: those who were enrolled, and those who were not randomised (and reason). The number and percentage of patients within each treatment group will be presented by the following categories: randomised, received study treatment, did not receive study treatment (and reason), completed study treatment, discontinued study treatment (and reason), completed study treatment but withdrawn from study, discontinued study treatment but completed study, discontinued study treatment and withdrawn from study, completed study, and withdrawn from study (and reason).

The number of patients randomised by country/region and centre will be summarised by treatment group using the FAS.

Kaplan-Meier plots will be produced summarising separately the time (in weeks) to study treatment discontinuation and to premature study withdrawal.

- Time to study treatment discontinuation = [date of last dose of study treatment - date of first dose of study treatment] + 1. Patients who did not prematurely discontinue study treatment will be censored at the date of last dose of study treatment.
- Time to premature study withdrawal = [date of study withdrawal – date of randomisation] + 1. Patients who did not prematurely withdraw from study will be censored at the date of study completion.

4.2.2 Demography data and patient characteristics

Demography data such as age, gender, race, and ethnicity will be summarised by treatment group for all patients in the FAS and for patients in the FAS with baseline blood eosinophil count $<300/\mu\text{L}$ and baseline blood eosinophil count $\geq 300/\mu\text{L}$.

Age will be derived from (date of informed consent - date of birth + 1), rounded down to the nearest integer (in years). For patients in countries where partial date of birth is recorded, the date of birth will be imputed following the below rule and then used in the age derivation.

- For the date of birth missing the day, the missing day will be set to the first day of the month of birth.
- For the date of birth missing both the day and month, the date will be set to July 1st of the year of birth.

Various baseline characteristics will also be summarised by treatment group using the FAS. These include smoking status, medical and surgical histories, FEV₁ at baseline, and respiratory disease characteristics (including asthma duration, age at asthma diagnosis, the number of exacerbations in the previous 12 months, the number of exacerbations during

background ICS/LABA treatment in the previous 12 months, and the number of exacerbations resulting in hospitalisation in the previous 12 months).

The following baseline data will be summarised for all patients in the FAS and repeated for patients in the FAS with baseline blood eosinophil count <300/ μ L and baseline blood eosinophil count \geq 300/ μ L:

- Patient characteristics (weight, height, body mass index (BMI), and blood eosinophil count). Note: BMI will be calculated as: $BMI (kg/m^2) = Weight (kg) / [Height (m)]^2$.
- Pre-bronchodilator lung function data (FEV₁ [L], FEV₁ [% predicted normal (PN)], FVC [L], FVC [% PN], FEV₁/FVC [%], FEF 25-75% [L/S]).
- Reversibility.
- Home lung function (morning and evening PEF)
- ACQ-6 score and total asthma symptom score
- Respiratory disease characteristics

Medical and surgical histories will be summarised by MedDRA Preferred Term (PT) within System Organ Class (SOC).

4.2.3 Prior and concomitant medications

The number and percentage of patients taking maintenance asthma medications at baseline, including ICS/LABA fixed dose combinations, will be summarised. For those patients taking ICS with or without OCS at baseline, the converted dose will be summarised for ICS and OCS. The number and percentage of patients taking at least one maintenance asthma medication at baseline in addition to ICS/LABA will be displayed. The total daily ICS dose (converted) at baseline will be further classified as medium dose or high dose according to Appendix E of the CSP. The number of patients taking maintenance ICS at baseline will be summarised in a separate table by ATC classification code and preferred term, with total daily dose (non-converted) at baseline summarised for each preferred term. A similar table will be produced to summarise total daily dose of maintenance OCS at baseline.

The number and percentage of patients who take prior medications, those who take allowed concomitant medications during the on-treatment period and those who take disallowed concomitant medications during the on-treatment period, will be separately presented by treatment group. Concomitant medication during the post-treatment period will only be listed. Disallowed medications are defined as prohibited/restricted medications according to Appendix F of the CSP, which will be identified following a physician review prior to database lock. Prior and concomitant medications will be classified according to WHO Drug Dictionary. The summary tables will present data by preferred term within ATC code.

Total OCS dose (converted) and total number of OCS treatment days associated with asthma exacerbations during the 48-week treatment period will be summarised descriptively by treatment group for patients with baseline blood eosinophil count $\geq 300/\mu\text{L}$ as well as for patients with baseline blood eosinophil count $< 300/\mu\text{L}$, from the FAS.

4.2.4 Study Treatments

4.2.4.1 Exposure

Exposure to IP will be calculated in days as:

$$\text{Date of last dose of IP} - \text{date of first dose of IP} + 1;$$

and will be summarised descriptively by treatment group using the safety analysis set.

4.2.4.2 Compliance

Study treatment compliance will be summarised descriptively for all patients, patients with baseline blood eosinophil count $< 300/\mu\text{L}$ and $\geq 300/\mu\text{L}$ in the FAS respectively and will be calculated as:

$$(\text{Total number of IP doses administered} / \text{total number of IP doses expected}) \times 100\%.$$

For patients who discontinue IP early, the number of expected dosing occasions will be calculated as the number of dosing visits up to and including the last available dosing visit for that patient.

4.2.5 Primary outcome variable

4.2.5.1 Primary analysis

The primary efficacy variable is the annual asthma exacerbation rate, and the primary analysis is to compare the annual asthma exacerbation rate of benralizumab group with placebo group in patients in the FAS with baseline blood eosinophil counts $\geq 300/\mu\text{L}$.

The primary analysis will include all data captured during the 48-week treatment period regardless of whether study treatment was prematurely discontinued, or delayed, and/or irrespective of protocol adherence. The details regarding the estimand for the primary endpoint are specified in Appendix 8.6.

Annual exacerbation rate in the benralizumab group will be compared to annual exacerbation rate in the placebo group using a negative binomial model. The response variable in the model will be the number of asthma exacerbations experienced by a patient over the 48-week treatment period. The model will include covariates of treatment group, region (China/Non-China), number of exacerbations in the year before the study, and the use of maintenance oral corticosteroids (yes/no). The logarithm of the follow-up time (as defined in Section 3.2) will be used as an offset variable in the model to adjust for patients having different exposure times during which the events occur.

This negative binomial model will be used to perform the hypothesis testing as specified in Section 4.1.1. The estimated treatment effect (i.e., the rate ratio of benralizumab versus placebo), corresponding 95% confidence interval (CI), and two-sided p-value for the rate ratio will be presented. In addition, the annual exacerbation rate (both crude and model-estimated rates) and the corresponding 95% CI (for model-estimated rates only) within each treatment group and the absolute difference between treatment groups with the corresponding 95% CI will be presented. The model-estimated annual exacerbation rate in each treatment group will be estimated via marginal standardisation method ([Bartlett, 2018](#)).

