1.2 Study design

This is a randomised, double-blind, parallel group, placebo-controlled study designed to evaluate the efficacy and safety of a fixed 30 mg dose of benralizumab administered subcutaneously for patients with a history of asthma exacerbations and uncontrolled asthma receiving medium to high-dose ICS/LABA with or without OCS and additional asthma controllers.

Approximately 666 patients will be randomised, of which at least 70% patients will be from China (including the mainland of China and Taiwan). The randomisation will be stratified by country/region (the mainland of China, Taiwan, South Korea or Philippine), age group (adult or adolescent), and peripheral blood eosinophil count at time of Visit 1 (<300 or \geq 300 cells/ μ L).

All the patients will be randomised to either placebo or benralizumab in a 1:1 ratio, every 4 weeks for the first 3 doses and then every 8 weeks thereafter. Study recruitment will be closed when recruitment is closed for all strata, based on the following strata closure process:

1. The eosinophil <300/ μ L stratum will be closed to the patients from China when the total number of Chinese patients in the eosinophil <300/ μ L stratum reaches approximately 166.
2. The eosinophil <300/ μ L stratum will be closed to the patients from all countries when the total number of patients in the eosinophil <300/ μ L stratum reaches approximately 222.
3. The whole study will be closed for recruitment when the total number of patients in the eosinophil \geq 300/ μ L stratum reaches approximately 444, with at least 70% Chinese patients in the stratum.

After initial enrolment and confirmation of entry criteria, patients will proceed to the run-in period of a minimum 4 weeks to allow adequate time for all of the eligibility criteria to be evaluated. Patients who meet eligibility criteria will be randomised to a 48-week treatment period. Patients will be maintained on their currently prescribed medium to high-dose ICS/LABA therapy and other asthma controllers, without change, from visit 1 until the end of the study.

A follow-up visit will be conducted at Week 56.

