4. ANALYSIS METHODS

4.1 General principles

In general, the analysis of the primary and secondary efficacy endpoints will include all data captured during the 48-week double-blind treatment period, defined as the period from randomisation at visit 4 and the conclusion of visit 17 (Week 48), inclusive. This includes data regardless of whether study treatment was prematurely discontinued, or delayed, and/or irrespective of protocol adherence, unless the patient withdraws consent/assent to study participation. In general, the analysis of safety endpoints will include all data captured during the on-study period, defined as the period from first dose of IP administration and the conclusion of the follow up visit (Week 56), inclusive.

The data analyses will be conducted using the SAS[®] System (SAS Institute Inc., Cary, NC). All SAS[®] programs used to generate analytical results will be developed and validated according to AstraZeneca SAS[®] programming standards and validation procedures.

Summary data will be presented in tabular format by treatment group. Categorical variables will be summarised by the number and percentage of patients in each category. Continuous variables will be summarised by descriptive statistics including number of observations (n), mean, standard deviation (SD), median, and range. All data will be listed.

All hypothesis testing will be reported using 2-sided tests. All reported p-values will be nominal (i.e., not multiplicity adjusted) and will be rounded to 4 decimal places. Statistical models will use stratification factors of region (China or non-China) and baseline blood eosinophil count ($<300/\mu\text{L}$ or $\geq 300/\mu\text{L}$), see Section 3.1.1 for details.

The absolute change from baseline is defined as in Section 3.1.2. Percent change from baseline is computed as $[(\text{post-baseline value} - \text{baseline value})/\text{baseline value}] \times 100\%$. If either a post-baseline value or the baseline value is missing, the absolute change from baseline value and the percent change from baseline will also be set to missing. Additional details regarding the definition of baseline are provided in Section 3.1.1.

Demography and baseline characteristics will be summarised by treatment group for the FAS. In the event that there are major differences between the FAS and safety analysis set, these summaries will also be repeated for the safety analysis set.

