4.2.6.1 Proportion of patients with ≥ 1 asthma exacerbation

The proportion of patients with ≥ 1 asthma exacerbation during the 48-week treatment period will be addressed as a supportive variable to the primary objective for patients with baseline blood eosinophil count $\geq 300/\mu\text{L}$. The proportion in benralizumab group will be compared with the proportion in the placebo group using a Cochran–Mantel–Haenszel test controlling for region (China/Non-China), number of exacerbations in the previous year (2, ≥ 3 exacerbations), and the use of maintenance oral corticosteroids (yes/no).

The results of the analyses will be presented using the odds ratio, together with associated 95% CI and 2-sided p-value for benralizumab versus placebo. The number and percentage of patients with ≥ 1 asthma exacerbation will also be summarised by treatment group.

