4.2.6.2 Time to first asthma exacerbation

Time to first asthma exacerbation will be analysed as another supportive efficacy variable to the primary objective to explore the extent to which treatment with benralizumab delays the time to first exacerbation compared with placebo. A Cox proportional hazard model will be fitted to data with the covariates of treatment group, region (China/Non-China), number of exacerbations in the previous year, and the use of maintenance oral corticosteroids (yes/no).

Results of these analyses will be summarised via the hazard ratio, with corresponding 95% CI and p-value for patients with baseline blood eosinophil count $\geq 300/\mu\text{L}$.

Time to first asthma exacerbation will be displayed graphically using a Kaplan-Meier plot, separately for patients with baseline blood eosinophil count $\geq 300/\mu\text{L}$ and $< 300/\mu\text{L}$.

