4.2.6.3 Pre-bronchodilator FEV₁ measured at the study centre

Change from baseline in pre-bronchodilator FEV₁ at Week 48, in the baseline blood eosinophil count $\geq 300/\mu\text{L}$ group, is a multiplicity protected key secondary endpoint (Section 4.1.1). The details regarding the estimand for the key secondary endpoint are specified in Appendix 8.6.

Change from baseline in pre-bronchodilator FEV₁ at Week 48 will be compared between the benralizumab group and the placebo group using a mixed-effects model for repeated measures (MMRM) analysis on patients with a baseline pre-bronchodilator FEV₁ assessment and at least 1 post-baseline pre-bronchodilator FEV₁ assessment.

The dependent variable will be the change from baseline in pre-bronchodilator FEV₁ at each post-baseline protocol-specified visit (up to and including the EOT visit). Treatment group will be fitted as the explanatory variable, region (China/Non-China), the use of maintenance oral corticosteroids (yes/no), visit, and treatment*visit interaction as fixed effects factors and baseline pre-bronchodilator FEV₁ as a continuous covariate. The variance-covariance matrix will be assumed to be “unstructured”. If the model does not converge then the “Toeplitz”, “first-order autoregressive”, “compound symmetric”, “variance components” variance-covariance matrix will be used instead sequentially. The model is:

*Change from baseline in pre-bronchodilator FEV₁ = Treatment group + baseline pre-bronchodilator FEV₁ + region (China/Non-China) + use of maintenance oral corticosteroids (yes/no) + visit + treatment*visit*

Results will be presented in terms of least square means (LSMEANS), treatment group differences in LSMEANS, corresponding 95% CIs and p-values. The OBSMARGINS option in LSMEANS statement in SAS will be used to specify different weighting scheme for computing the LSMEANS.

The above analysis will be repeated for the following as supportive analysis:

- Baseline blood eosinophil count $< 300/\mu\text{L}$

- Cumulative baseline blood eosinophil count categories ($\geq 150/\mu\text{L}$, $\geq 200/\mu\text{L}$, $\geq 250/\mu\text{L}$, $\geq 300/\mu\text{L}$, $\geq 350/\mu\text{L}$, $\geq 400/\mu\text{L}$, $\geq 450/\mu\text{L}$, $< 150/\mu\text{L}$, $< 200/\mu\text{L}$, $< 250/\mu\text{L}$, $< 300/\mu\text{L}$, $< 350/\mu\text{L}$, $< 400/\mu\text{L}$, $< 450/\mu\text{L}$)

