4.2.13 China subpopulation analysis

China subpopulation analysis will be performed using the same methodology as for the overall study population. Region (China or non-China) will not be adjusted in the statistical models as for the overall study population, because all patients in the China subpopulation are from China (see Section 2.2 for the definition of China subpopulation).

The key efficacy analyses of the primary endpoint (annual asthma exacerbation rate), key secondary endpoints (pre-bronchodilator FEV₁, total asthma symptom score) and other selected secondary endpoints will be repeated for China subpopulation. In general, the sensitivity analyses will not be repeated for China subpopulation. All statistical analyses for China subpopulation will be considered exploratory. No adjustment for multiplicity will be made and so the multiple testing procedure as described in Section 4.1.1 will not be followed for China subpopulation analyses.

The patient disposition and selected baseline data will be summarised for China subpopulation. The key safety analyses as outlined in Section 4.2.10 will be repeated for China subpopulation. Selected PK and immunogenicity analyses will be repeated for China subpopulation as well.

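### Age group is a randomisation factor but is in no efficacy model, and the China models have no mainland/Taiwan term: a small loss of precision, not a threat to validity

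*SAP*

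**What the plan says.** Section 1.2 of the SAP sets the design: "The randomisation will be stratified by country/region (the mainland of China, Taiwan, South Korea or Philippine), age group (adult or adolescent"), and Visit 1 eosinophil count below or at least 300 cells/µL. On allocation it says "All the patients will be randomised to either placebo or benralizumab in a 1:1 ratio".

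Section 4.1 states the modelling principle: "Statistical models will use stratification factors of region (China or non-China) and baseline blood eosinophil count". Age group is not in that list, and four-level country/region has become China versus non-China. The individual models follow suit:

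- Section 4.2.5.1 (negative binomial, primary): "The model will include covariates of treatment group, region (China/Non-China), number of exacerbations in the year before the study", plus maintenance oral corticosteroids.
- Section 4.2.6.1 (Cochran–Mantel–Haenszel): "controlling for region (China/Non-China), number of exacerbations in the previous year", plus maintenance oral corticosteroids.
- Section 4.2.6.2 (Cox): "A Cox proportional hazard model will be fitted to data with the covariates of treatment group, region (China/Non-China"), prior exacerbations and maintenance oral corticosteroids.
- Section 4.2.6.3 (MMRM for FEV₁, reused for the symptom score and other continuous endpoints): "Treatment group will be fitted as the explanatory variable, region (China/Non-China), the use of maintenance oral corticosteroids (yes/no"), visit, treatment by visit, and baseline FEV₁.
- Sections 4.2.7.5 and 4.2.7.6 (logistic): treatment, region, baseline value and maintenance oral corticosteroids.

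Section 4.2.13, on the China subpopulation: "Region (China or non-China) will not be adjusted in the statistical models as for the overall study population". The reason given is that everyone in it is from China. Section 2.2 defines that subpopulation as mainland plus Taiwan.

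**The concern.** An analysis that follows stratified randomisation normally carries the stratification factors. Stratifying balances a prognostic factor between arms. If the model leaves that factor out, its variance stays in the error term, and the model standard error is larger than the design warrants.

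The confirmatory tests in Section 4.1.1 are confined to patients with at least 300 eosinophils/µL, where the eosinophil stratum is constant. Two-level region is then the only stratification factor left in the model. The amendment history explains why country became region (few patients outside China). That reason covers neither the omission of age group nor the merging of Taiwan with the mainland, and Section 6 is silent on both.

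Age group has no other role in the efficacy models either. The age subgroups in Section 4.2.5.3 start at 18 years, so adolescents fall in no category, while Section 1.3 says they are part of the efficacy analyses. What is at stake is some precision in the primary and key secondary tests, and a covariate choice left without a stated reason.

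**Working it through.** **1. The plan's own figures.** 2 × 222 = 444 and 2 × 111 = 222, so 444 + 222 = 666, which agrees with Section 1.3. The 90% power figure cannot be reproduced because its inputs are blacked out. As a plausibility check, n per arm = (z₀.₉₇₅ + z₀.₉₀)² × [1/(λ₀t) + 1/(λ₁t) + 2k] / (ln RR)², with t = 48/52.18 years and no dropout. Assumed values RR 0.65, k 0.8, placebo rate 1.2/year give 10.507 × (0.906 + 1.394 + 1.6)/0.1856, or 221 per arm. So 222 is plausible but not verified.

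**2. Effect of the omitted terms on the primary model.** Simulation with 1,500 trials per scenario, blocks of 4 within country/region by age strata, placebo rate 1.0/year and k = 0.8. Model A has treatment and two-level region. Model B adds age group and the full country/region levels. Both leave out prior exacerbations and oral corticosteroid use. The adolescent share, Taiwan's share of China patients and the rate multipliers are assumptions; the SAP gives none of them.

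| Population, n | Adolescents (rate multiplier) | Taiwan (rate multiplier) | Mean SE A | Mean SE B | A/B |
|---|---|---|---|---|---|
| Overall, 444 | 3% (1.5) | 10% (1.0) | 0.1281 | 0.1275 | 1.005 |
| Overall, 444 | 3% (0.5) | 10% (0.6) | 0.1311 | 0.1301 | 1.008 |
| Overall, 444 | 10% (2.0) | 15% (0.5) | 0.1315 | 0.1278 | 1.029 |
| China, 311 | 3% (0.5) | 15% (0.5) | 0.1634 | 0.1612 | 1.014 |
| China, 311 | 10% (2.0) | 20% (0.4) | 0.1662 | 0.1598 | 1.040 |

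(311 = 0.70 × 444.)

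- Type I error, overall: 4.5–4.9% for A and 4.5–4.7% for B.
- Type I error, China: 5.0–5.5% for A and 5.7–5.8% for B. Monte Carlo error is about 0.6 points.
- Power at RR 0.65, overall: 86.3% against 86.4% in the second scenario, and 87.5% against 88.5% in the third. Monte Carlo error is about 0.9 points on each figure.

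**3. Age group alone.** A separate simulation (about 400 trials per scenario; 222 per arm, placebo rate 1.0/year, RR 0.62, dispersion 1, adolescents at twice the adult rate) added only the age term. The mean SE went from 0.147 to 0.146 with 5% adolescents, 0.147 to 0.145 with 10%, and 0.146 to 0.143 with 15%. These are falls of about 0.7%, 1.4% and 2.1%. At 3% there was no gain, and the age term was sometimes not estimable.

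**4. FEV₁.** The share of variance removed is q(1−q)d²/SD², where q is the adolescent share and d the adult/adolescent difference in change. With SD 0.4 L assumed:

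- q = 5%, d = 0.1 L: 0.0475 × 0.01/0.16 = 0.3%
- q = 15%, d = 0.3 L: 0.1275 × 0.09/0.16 = 7.2%
- q = 3%, d = 0.3 L: 0.0291 × 0.09/0.16 = 1.6%

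On the SE scale, 1 − √(1 − 0.072) = 3.7% at the top and about 0.15% at the bottom. The formula takes no account of baseline FEV₁, which is already in the MMRM, so these are generous figures.

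**5. What the SAP implies about the adolescent share.** The amendment history attributes the changed subgroup categories for age, BMI and prior exacerbations to small expected numbers. Section 6 shows that the under-18 category was among those removed. At 3%, the primary population would contain 0.03 × 444 ≈ 13 adolescents.

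**The case against.** The case against acting is strong on size. A reader might infer from the mismatch that the standard errors are wrong in a way that endangers the primary test. They are not: the error is conservative, and simulated type I error in the overall model stays at or below 5%.

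A reader might also take the upper figures (3% in SE, 7% of FEV₁ variance) as the likely gain. The documents do not support that. The amendment history and the dropped under-18 subgroup point to few adolescents, where the gain is nil or close to it. The 2.9% figure comes from adding age and all country levels together, so it cannot be credited to age alone. No text in the SAP supports a doubled adolescent rate. The simulation in step 2 omitted prior exacerbations and oral corticosteroid use, both already in the primary model, so the real gain could be smaller.

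Pooling country into region is a recorded decision aligned with the protocol. Section 6 names no departure for the primary covariates, so the unseen protocol may fix them. The China analyses are exploratory without multiplicity control, and the simulations show no type I error benefit there.

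All of this stands, and it limits the point to a small one. It does not supply a reason for leaving a randomisation factor out of the analysis, and the SAP gives none.

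**Conclusion.** The point holds as a mismatch between design and analysis with a small cost in precision. Age group is stratified on and then absent from Section 4.1 and every efficacy model; the China models carry no mainland/Taiwan term.

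Under the assumed inputs the overall model's standard error is about 0 to 3% too large, and near nil if adolescents are about 3% or fewer. Power loss is about 0 to 1 point. In the exploratory China models the excess is 1.4 to 4.0%, under assumed Taiwan shares and rates. All sizes rest on adolescent and Taiwan counts that the SAP does not give. Validity of the confirmatory tests is not in question.

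**What to change.** - **Section 4.1:** list age group (adult/adolescent, as randomised) with the other stratification factors.
- **Sections 4.2.5.1, 4.2.6.2 and 4.2.6.3, and the regression models built on them:** add the age term. The imputation in Appendix 8.1.1.3 starts from the primary model and would inherit it.
- **Section 4.2.6.1:** leave the Cochran–Mantel–Haenszel test as it is. Its strata were already pooled for sparseness, and age strata would undo that.
- **Fallback, fixed before unblinding:** drop the term if either level has fewer than a stated minimum number of patients, arms pooled, in the analysis population (for example 5 to 10, which is 1.1 to 2.3% of 444). The rule should use blinded patient counts only. A rule based on events would make the confirmatory model depend on the outcome.
- **Section 4.2.13, lower priority:** use mainland/Taiwan in place of the dropped region term, under the same count rule.

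The cost is SAP wording and one model term, made while the study is blinded. There may be little or no gain if adolescents are very few. If the protocol fixes the covariates, the change also needs an entry in Section 6.
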